6 STUDY INTERVENTION(S) OR EXPERIMENTAL MANIPULATION(S)

6.1 STUDY INTERVENTION(S) OR EXPERIMENTAL MANIPULATION(S) ADMINISTRATION

6.1.1 STUDY INTERVENTION OR EXPERIMENTAL MANIPULATION DESCRIPTION

ACTIVE INTERVENTION

High intensity medical weight loss: Participants randomized to the HIWL treatment group will be placed on a meal replacement-based weight loss protocol. [name] will oversee the medical management team and implementation of this protocol at the Weight Management Center. He serves as the medical director for medical weight management and has over 13 years of experience treating a wide range of patients with a low calorie meal replacement protocol. Participants will consume a minimum of 80 grams of protein daily in 4-5 servings of meal replacement. Minimum caloric intake will be 960 kcal/day with adjustments to intake made based on BMI and activity levels, holding the percent of calories from protein constant at 35%. The meal plan provides 100% of daily recommended needs for micronutrients. Meal replacements will be supplied at no cost to the participant at weekly clinic visits. Meal replacements are in the form of shakes, soups, and meal bars. Participants will begin to incorporate food into their routine beginning at week 13 with guidance from a dietitian. From weeks 13-24, caloric prescriptions will be between 1100 to 1600 kcal/day, using a combination of meal replacements and food, for continued weight loss. Beyond week 25, caloric intake will be individually tailored to achieve continued gradual weight loss or maintenance of body weight based on individual weight loss goals. Minimum caloric intake during this third treatment segment will be 1200 kcal/day. Participants will be seen by a study team clinician weekly for the first 4 weeks of the treatment plan. This weekly follow up will allow the medical weight loss team the opportunity to assess early treatment response, assess for side effects, and adjust medications to avoid hypoglycemia, hypotension, and/or dehydration. The first month of treatment is also critical to identify potential non-responders and alter their treatment plan early on. Research suggests that treatment non-response in the first 4-12 weeks is associated with poor weight loss outcomes.^{20,21} Beyond this first month of scripted intervention, the team will use information from the digital platform (described below) to dictate the type and intensity of follow up. Key factors that will influence the treatment plan are treatment response including pace of weight loss and changes in glycemic control; engagement in key behaviors including self-monitoring and physical activity; and complexity of the participant's medical regimen including use of insulin, anti-hypertensives, or other medications that we adjust during weight loss.

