Demographics: Demographic information including sex, race/ethnicity, and date of birth (age) will be captured at the first screening visit during verification of eligibility. Medical history including date of

diabetes diagnosis (duration of diabetes) and co-morbid conditions will be captured by interview and verification from the medical record when available.

Dietary intake: To assess **dietary intake**, we will use NCI's automated, self-administered 24-hour dietary recall, the Automated Self-Administered 24-hour (**ASA24**®) dietary assessment tool (version: ASA24-2018). The ASA24-2018 will be completed on three, non-consecutive days (including one weekend day) at baseline (pre-randomization), and again at months 3, 6, and 12. The ASA24-2018 is available for use on computers and mobile devices. At the baseline visit, participants will complete one ASA24 assisted by a research staff member. They will then be asked to complete a second and third ASA24 during run-in, on their own, as a part of the baseline assessment. During office visits at each relevant follow-up time point (3, 6 and 12 months), participants will again complete the ASA24. Following each of these visits, a staff member will contact participants within six days (on a randomly selected day) to inform them to complete 2 additional dietary recalls and will offer to conduct the recall over the phone if needed (the ASA24 performs equally well as a self- or interviewer- administered questionnaire).^{23,24} Follow-up reminder calls will be made to encourage completion of the recalls if not completed within 24-hours following a contact. Using the ASA24 data from each time point (baseline, 3, 6, and 12 months), specific outcomes of interest will include: **total daily energy intake** (kcal; averaged across 3 days), **macronutrient composition** of diet (%Carbohydrate/Fat/Protein; averaged across 3 days), **number of eating episodes** per day, and **Healthy Eating Index (HEI)-2015** score (a validated summary measure of dietary quality, rated on a 100-point scale,^{25,26} which is sensitive to change with dietary intervention^{26,27}, and can be calculated using publicly-available SAS code from the ASA24 website).

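### Month-3 diet recalls 2 and 3 are requested after the week-12 visit, so the 3-day average can straddle the week-13 diet change, and only in the two active arms

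*Combined protocol and SAP*

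**What the plan says.** Section 8.1 (Dietary intake) sets one rule for all time points: "The ASA24-2018 will be completed on three, non-consecutive days (including one weekend day) at baseline (pre-randomization), and again at months 3, 6, and 12". At baseline, one recall is done with staff at the visit and two follow during run-in, so all three precede randomization.

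At follow-up the first recall belongs to the visit: "During office visits at each relevant follow-up time point (3, 6 and 12 months), participants will again complete the ASA24". The other two are both requested at one later contact: "Following each of these visits, a staff member will contact participants within six days (on a randomly selected day". Late completion is handled by chasing: "Follow-up reminder calls will be made to encourage completion of the recalls if not completed within 24-hours following a contact". No last acceptable date is given. Energy intake is summarised as "kcal; averaged across 3 days", and macronutrient composition is averaged in the same way. Eating episodes and the diet-quality score come from the same recalls.

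The schedule in Section 1.3 puts the 3-month dietary assessment at week 12. For the active intervention, Section 6.1.1 sets a minimum of 960 kcal/day from meal replacements in the first segment, adjusted for BMI and activity. Then: "Participants will begin to incorporate food into their routine beginning at week 13 with guidance from a dietitian". The prescription for weeks 13-24 is 1100-1600 kcal/day from a mix of meal replacements and food. Section 4.1 gives HIWL + CGM the same intervention. For DSME, Section 6.1.1 describes a single energy-deficit prescription with no phases.

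**The concern.** A 3-day average is interpretable if the three days come from the same diet regimen. At month 3 the first recall sits at the end of the meal-replacement segment, and the other two are requested in the days when the next segment may already have begun. If so, the active-arm value describes neither segment, while the DSME value describes one unchanged prescription. The mixing is tied to treatment arm, so it enters any between-arm comparison of month-3 diet.

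Month 3 is also the first scheduled recall after the meal-replacement segment starts, and hence the first opportunity for the recalls to describe it. Besides energy, a move from meal replacements to food can change eating episodes, macronutrient shares and diet quality, all of which Section 8.1 lists as outcomes of interest.

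**Working it through.** The plan gives no figure on this point, so there is none to reproduce. The check is a calendar enumeration followed by simple averaging.

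**Inputs from the documents**
- Month-3 visit at week 12 (Section 1.3), taken as day 12 × 7 = 84.
- One contact on a random day within six days after the visit, covering both remaining recalls (Section 8.1).
- Active arms: first-segment minimum 960 kcal/day; 1100-1600 kcal/day in weeks 13-24 (Section 6.1.1).
- Summary: mean of three days (Section 8.1).

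**Assumptions, because the documents are silent**
- Contact day c is equally likely to be 1 to 6 days after the visit.
- Recall 2 is done on the contact day. Recall 3 is done g days later, with g = 2, or spread evenly over 2-4 or 2-7.
- Each recall covers the same day (L = 0) or the previous day (L = 1).
- The days covered are then 84 − L, 84 + c − L and 84 + c + g − L.

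**How often phases mix**
- *Week 13 starts on day 85.* Recall 1 covers day 84 or earlier. Recall 3 covers at least day 84 + 1 + 2 − 1 = 86. Every adherent active-arm participant mixes phases: 100%.
- *Week 13 starts on day 84.* With L = 1, recall 1 covers day 83 and recall 2 covers day 84 or later: 100%. With L = 0, all three days are second-segment: 0% mixing, but the set then contains no first-segment day.
- *Week 13 means day 91 (13 completed weeks).* Recall 2 covers at most day 84 + 6 = 90, so only recall 3 can cross, when c + g − L ≥ 7.
  - Lowest case, L = 1 and g = 2: needs c = 6, so 1/6 = 17%.
  - Highest case, L = 0 and g over 2-7: for c = 1 to 6 the qualifying values of g number 2, 3, 4, 5, 6 and 6, so 26/36 = 72%.
  - Restricting contacts to weekdays, with visits spread evenly over Monday to Friday, stays within this range.

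**Illustrative size for energy intake**

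With k second-segment days, first-segment intake P1 and second-segment intake P2, the shift from the first-segment value is (k/3) × (P2 − P1).
- k = 2, P1 = 960: (2/3) × (1100 − 960) = 93 and (2/3) × (1600 − 960) = 427 kcal/day, giving 3-day means of 1053 and 1387.
- k = 1, P1 = 960: (1/3) × 140 = 47 and (1/3) × 640 = 213 kcal/day.
- k = 2, P1 = 1100 instead: (2/3) × 0 = 0 and (2/3) × 500 = 333 kcal/day.

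On the day-91 reading at most one day crosses under these assumptions. With P1 = 960, the average shift across an active arm would be between (1/6) × 47 ≈ 8 and (26/36) × 213 ≈ 154 kcal/day.

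**Months 6 and 12**
- The week-24 visit closes the second segment. Section 6.1.1 describes the third as beyond week 25 and does not place week 25 itself, so a similar straddle may arise. Intake in the third segment is individually tailored, so no size can be given.
- The week-52 visit is the closeout visit (Section 1.3). Recalls 2 and 3 at month 12 are therefore requested after closeout. No diet change is stated there, so this is a question of completing follow-up and not of mixing.

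**The case against.** A reader might infer that mixing is certain. The documents do not support that: they define neither the numbering of study weeks nor a recall window, and Section 6.1.1 has participants beginning to add food, not switching on one day. This objection stands, and it is why the frequency is given as a range. That said, weeks 13-24 read most naturally as the 12 weeks following weeks 1-12, which favours the near-universal case.

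The size is open to the objection that 960 kcal is a minimum, individually adjusted, and that the 427 kcal figure pairs the lowest first-segment prescription with the highest second-segment one. That also stands. The figures are illustrations at prescribed intake and shrink as P1 rises.

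A reader might also infer that follow-up averages will often lack a weekend day. The text does not support this: the requirement for non-consecutive days with one weekend day applies explicitly at months 3, 6 and 12, so no set lacks a weekend day if the protocol is followed. What remains is that a single random-day contact for two recalls does not show how the rule will be met. That gap is common to all arms, and the manual of procedures promised in Section 6.2.1 could close it.

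Baseline collection also runs visit first, two recalls afterwards, so follow-up is not out of step in its order. The relevant difference is that the baseline set is complete before randomization, whereas the month-3 set can run past a change in prescription.

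Finally, dietary intake is not an endpoint in Section 3, Section 9.4.1 does not name it, and active-arm engagement is monitored weekly through the platform (Section 6.4). This limits the importance of the point but does not remove the timing problem.

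**Conclusion.** The point holds as a low-priority flaw in measurement timing. Following Section 8.1 as written, the month-3 recall averages can combine two diet segments in HIWL and HIWL + CGM and not in DSME. Mixing is near-universal among adherent participants if week 13 begins right after the week-12 visit (the exception is a day-84 start with same-day recall), and about 17-72% if week 13 means day 91. The latter range rests on the assumed contact and spacing pattern. With first-segment intake at 960 kcal/day, the 3-day energy mean is 93-427 kcal/day above the first-segment value with two later-phase days, and 47-213 with one.

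A similar boundary is possible at month 6, and at month 12 two of the three recalls follow closeout. A reader might take this as a threat to the weight result. It is not: body weight, HbA1c, remission and the power statement in Section 9.2 do not depend on the recalls.

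**What to change.** In Section 8.1, require all three follow-up recalls to be completed in a stated window, for example 7-10 days, ending at the week 12, 24 and 52 visits. Each set should fall within one diet segment, just as all baseline recalls precede randomization. Within the window, pre-assign each participant's days to meet the existing rule (non-consecutive, one weekend day) and send a separate prompt for each recall.

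State how study weeks are numbered and which day a recall covers. Record the date of each recall, so that a set collected around a rescheduled visit can be recognised if it crosses a segment boundary.

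The cost is wording in the protocol and manual, earlier scheduling and possibly one more prompt per time point. The number of recalls stays the same, and no diet prescription is altered.

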4.4 END-OF-STUDY DEFINITION

This study will be carried out to completion, defined as 12 months of follow up for all enrolled participants.

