Physical activity: We will use pedometers to assess objective physical activity (PA) – operationalized as **daily step counts** – at baseline, 3, 6, and 12 months. Although accelerometry is the gold standard for objective PA measurement,²⁸ pedometers have 99.8% step count accuracy, particularly when worn at the hip.^{29,30} For our study, participants will be fitted with a pedometer and asked to wear it for all waking hours (except while bathing or water activities) over their right hip for 7 consecutive days at each relevant time point in follow-up. At the end of the 7th day, participants will open the unit, record the final step count, and return the pedometer to WFSOM via a pre-stamped mail envelope. **Self-report:** In order to compare our results with the extant literature that has used self-reported PA outcomes, we will also include the short form of the IPAC, a self-report instrument with good reliability (Spearman's rho=0.8) and criterion validity comparable to other self-report instruments.³¹

Diabetes medication class/dose: All medications will be assessed quarterly as previously described. Variables of interest include medication name, total dose, and class of medication at baseline and longitudinal changes during the trial follow up.

Healthcare utilization and quality of life: To capture differences in quality of life associated with the intervention arm, we will use EuroQol's EQ-5D-5L instrument as the quality measure³². This instrument takes responses to five questions on mobility, self-care, ability to perform usual activities, pain, and anxiety/depression to produce a validated quality score (0 to 1). This instrument will be administered at baseline and at the end of the study (12 months). We anticipate no patient deaths during the study period; as such, we will treat the difference in the quality score at the end of the study period and at baseline as the change in the quality of life year (QALY). For instance, if the quality score is 0.4 at baseline and 0.6 at the study-end, the change in the quality of life will be 0.2 QALYs.

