Cost data: There will be two cost categories: *intervention costs* and *healthcare utilization costs*. Intervention costs will cover the costs incurred in the implementation of the intervention. This will include, for the HIWL arm, the provider visits (in-person and telemedicine) associated with the intervention will be assessed in terms of the insurance reimbursement (\$). For intervention services and resources not reimbursed by insurance (meals, software installation, staff time), we will use the micro-costing approach to aggregate the costs. As insurance reimbursement for the same service may vary by insurer, we will use Medicare fee-for-service reimbursement as the standardized rate so as to limit confounding arising from differences in insurer composition across intervention arms (ResDAC 2020). Patient out-of-pocket costs will also be included (e.g., insurance co-payments and deductibles). We will not include any costs relating to the research administration (e.g., staff time for data collection and analysis). For the HIWL+ CGM arm, we will include the cost of continuous glucose monitoring. Healthcare utilization costs will include healthcare services used during the study period but are not part of the interventions: hospitalizations, emergency department visits, outpatient visits, and prescription medications. Costs of these services will be assessed at Medicare rates. We will refer to the sum of the intervention and healthcare utilization costs as the *total costs*. Note that an intervention may lead to higher intervention costs compared to the control arm; however, if an intervention results in higher rates of diabetes remission, then healthcare utilization may be lower for the intervention cohort, compared to the control arm. The total cost captures the net change of the higher intervention and lower utilization costs.

Cost-effectiveness Outcomes: Our main outcome for cost-effectiveness analysis will be diabetes remission. We will compare the relative costs of achieving one additional remission using alternative interventions. As secondary outcomes, we will also examine the cost-effectiveness of (a) one percentage unit reduction in A1c and (b) one additional QALY.

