Cost-Effectiveness Analysis: The most commonly used measure of cost-effectiveness is the incremental cost-effectiveness ratio (ICER), defined as the ratio of between incremental costs (difference in total costs between intervention and control arms) and incremental diabetes remission (difference in the number of patients with remission in the intervention and control arms)³³. This measure is meaningful in contexts where an intervention increases total costs (since the denominator is expected to be positive, with higher diabetes remission in the intervention arm relative to the control arm). However, in our context where total costs include both intervention and non-intervention healthcare utilization, total costs for the intervention arm may be lower (e.g., if diabetes remission is accompanied by fewer emergency department visits or fewer medications). In this situation, we will report two measures: a) the average additional intervention cost for each additional diabetes remission achieved; and b) the average reduction in healthcare utilization cost for each additional diabetes remission achieved. For the secondary outcome of A1c reduction, we will similarly estimate the average cost of achieving one percentage point reduction in A1c and one additional QALY for each arm (Laiteerapong et al. . We will obtain 95% confidence interval of each estimate based on bootstrap resampling (Briggs et al. 1999). We will perform a variety of sensitivity analyses, including alternative healthcare reimbursement rates (e.g., 10 percent higher than Medicare rates).

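### The QALY rule takes the 12-month minus baseline EQ-5D-5L score as the QALY change, with no time weighting; under a linear rise it doubles the gain and halves the cost per QALY

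*Combined protocol and SAP*

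**What the plan says.** Section 8.1, in the paragraph on healthcare utilization and quality of life, defines the QALY change as a simple difference of two scores: "we will treat the difference in the quality score at the end of the study period and at baseline" as the change in QALYs. The worked example is that "if the quality score is 0.4 at baseline and 0.6 at the study-end, the change in the quality of life will be 0.2 QALYs". The only reason offered is "We anticipate no patient deaths during the study period". The same paragraph places the EQ-5D-5L at two time points, baseline and 12 months.

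The schedule of activities in Section 1.3 marks the EuroQOL-5D three times: at the second screening visit (T-2), at week 24 and at the end of the study. The last mark is read here as week 52; in the extracted text it sits one column past that header, which looks like a shift in extraction.

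The horizon is one year: Section 4.4 has the study run to completion, "defined as 12 months of follow up for all enrolled participants". On the use of the result, Section 8.1 makes remission the main cost-effectiveness outcome and then adds: "we will also examine the cost-effectiveness of (a) one percentage unit reduction in A1c and (b) one additional QALY".

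Section 9.4.1 defines the effect in the incremental ratio as the "difference in the number of patients with remission in the intervention and control arms". It then says that the cost of a one-point A1c reduction will be estimated in a similar way, together with that of "one additional QALY for each arm".

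**The concern.** A QALY is utility accumulated over time. A difference between two scores is a difference in utility level, and it becomes a number of QALYs only once one says how long each level was held. The absence of deaths removes the survival part of the calculation. It does not make a score measured at month 12 apply to the months before it, and no section states an assumption that it does.

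The QALY gain is the denominator of a planned cost-effectiveness result. If the gain is overstated, the cost per QALY is understated by the same factor. A reader who has only the baseline and 12-month scores cannot undo this, because the factor depends on what happened in between. The one intermediate measurement that would help, at week 24, is in the schedule but not in the rule.

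Two smaller points in Section 9.4.1 bear on the same analysis. An effect expressed as a count of remissions is sensitive to unequal numbers analysed, and the text does not make clear whether the A1c and QALY ratios are increments over DSME.

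**Working it through.** **Inputs.** Baseline score 0.4, final score 0.6 and stated change 0.2 QALYs (Section 8.1 example); horizon 1 year (Section 4.4); EQ-5D at baseline, week 24 and study end (Section 1.3). The documents give no utility path and no cost figure for the QALY analysis, so every path and cost below is an assumption.

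**The plan's own figure.** End minus baseline: 0.6 − 0.4 = 0.2. It reproduces.

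**Time-weighted gain, linear path.** Gain = area under the utility curve − baseline utility × 1 year = (0.4 + 0.6)/2 × 1 − 0.4 × 1 = 0.5 − 0.4 = 0.10 QALYs. Ratio 0.2/0.10 = 2.0. At fixed cost the cost per QALY is 0.10/0.2 = 0.50 of the area-based value. For example, an assumed incremental cost of $5,000 gives 5,000/0.2 = $25,000 per QALY under the rule and 5,000/0.10 = $50,000 by area.

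**Linear rise to 0.6 by time T (years), then plateau.** Gain = 0.2 × (1 − T/2).

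| Plateau from | Gain (QALYs) | Rule ÷ gain |
|---|---|---|
| Day 0 | 0.200 | 1.00 |
| Month 3 | 0.175 | 1.14 |
| Month 6 | 0.150 | 1.33 |
| Month 9 | 0.125 | 1.60 |
| Month 12 (linear throughout) | 0.100 | 2.00 |

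**Using the scheduled week-24 score, m.** Trapezoid through weeks 0, 24 and 52: gain = (0.4 + m)/2 × 24/52 + (m + 0.6)/2 × 28/52 − 0.4.

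| Assumed m | Gain (QALYs) | Rule ÷ gain |
|---|---|---|
| 0.40 | 0.054 | 3.7 |
| 0.50 | 0.104 | 1.9 |
| 0.60 | 0.154 | 1.3 |
| 0.70 | 0.204 | 0.98 |

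The rule reports 0.2 in all four cases.

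**Between arms.** Assume linear change in both arms, +0.20 in one and +0.05 in the other. The rule gives 0.20 − 0.05 = 0.15. By area the difference is 0.10 − 0.025 = 0.075. The factor of 2 does not cancel in the comparison.

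**Counts of remission.** With n analysed in each arm, total costs over counts is n × (mean cost difference) ÷ n × (difference in proportions), so n cancels and the count form does no harm. With unequal numbers it does not cancel. If the 20% loss allowed for in Section 9.2 fell on one arm only (assumed), 24 and 30 would be analysed. At an assumed 10% remission in both, the expected counts are 2.4 and 3.0, an apparent difference of 0.6 remissions where there is none.

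**The case against.** The best defence has four parts.

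- **The rule is openly stated and its subtraction is correct.** This stands: the fault is in the definition of the QALY change, not in the arithmetic.
- **The factor of 2 may be too pessimistic for this intervention.** Section 6.1.1 describes a front-loaded programme, with meal replacement to week 12, a mixed phase to week 24, then gradual loss or maintenance. If utility follows weight, which is an assumption, the early-plateau factors of 1.14 to 1.33 are nearer the mark. This stands as a limit on size. The rule is still not a QALY calculation.
- **Baseline is not ignored.** A change score already subtracts it, and the covariance analysis in Section 9.4.1 adjusts continuous 12-month outcomes for their baseline values in open-ended terms. This stands. Adjustment for baseline utility needs to be stated for an area-based QALY, but the present rule cannot be said to disregard baseline.
- **Section 9.4.1 already plans bootstrap intervals and sensitivity analyses, and gives two separate measures for the case of falling costs.** This stands. A cost-effectiveness plane or net monetary benefit would be a matter of preference.

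A reader might infer two stronger faults in Section 9.4.1. The first is that remission counts in 60 pooled HIWL participants will be set against 30 in DSME. The pooling appears in hypotheses H1, H2a and H2b (Section 9.1). The cost-effectiveness text never pools the active arms, Section 8.1 costs the CGM arm separately, and the design is 30 per arm. What remains is the risk from unequal analysed numbers. The second is that the phrase about each arm means within-arm average ratios. It follows an explicitly incremental ratio and is introduced as similar to it, so it may mean each active arm against DSME. It is ambiguous, not a demonstrated error.

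**Conclusion.** The QALY definition in Section 8.1 is wrong as written, because it drops the time dimension and the expected absence of deaths does not justify that. For a linear path in the protocol's own example, the gain is 0.10 QALYs against 0.2 stated, and the cost per QALY is halved if cost is held fixed.

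The size in practice is not known. A reader might infer that the rule always doubles the gain, that it is right only if the whole gain is present on day 0, or that the error is as large as fourfold and usually favours the costlier arm. The documents support none of these, since they give no utility path. A mid-study peak makes the rule about right or slightly too low (0.204 QALYs with a week-24 score of 0.70), and the largest factors need almost no gain in the first half of the year.

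Sections 8.1 and 1.3 also disagree on whether the EQ-5D is collected at week 24, whatever is decided about the formula.

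The consequence is confined. Section 3 lists this objective as tertiary/exploratory, and cost per QALY is a secondary outcome within it. The weight, HbA1c, remission and cost-per-remission results do not use the QALY.

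**What to change.** - **Section 8.1:** replace the end-minus-baseline rule and its example with each participant's trapezoidal area under the EQ-5D-5L curve through baseline, week 24 and week 52. Compare each active arm with DSME, adjusting for baseline utility.
- **Sections 8.1 and 1.3:** reconcile the EQ-5D time points so that both list the same three.
- **Section 9.4.1:** express remission as a proportion and cost as a mean per participant, so that unequal analysed numbers cannot distort the ratio. State that the cost per A1c point and per QALY are increments over DSME.

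The cost is revised wording and a little more analysis work. The schedule already includes the week-24 questionnaire, so no visit or instrument is added. The downside for the sponsor is that the cost per QALY will probably look less favourable, though this is not assured.
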